8 TOXICITIES TO BE MONITORED AND DOSAGE MODIFICATIONS

This study will utilize the CTC (NCI Common Toxicity Criteria) Version 3.0 for toxicity and Adverse Event reporting. A copy of the CTC Version 3.0 can be downloaded from the CTEP home page (http://ctep.cancer.gov). All appropriate treatment areas should have access to a copy of the CTC Version 3.0.

8.A ESHAP Toxicities & Dose Modification

In the case of multiple toxicities, dose modifications should be based on the most severe dose-limiting toxicity.

8.A.1 Hematologic Toxicity:

The ESHAP regimen should be given as described in Section 7.A if the granulocytes are > 1,500 cells/ μ L and the platelets are > 100,000 cells/ μ L by the time the next cycle is due. If the blood counts have not recovered, treatment should be delayed by an additional week and counts repeated unless low peripheral counts are due to tumor. If, after 2 weeks, counts have not yet recovered, the patient should be treated at 75% of the last dose received of etoposide and cytarabine.

8.A.2 Grade 3 or 4 Infection:

(NCI Common Toxicity Criteria Version 3.0) due to chemotherapy-related neutropenia requires a decrease in the doses of etoposide and cytarabine to 75% of the last dose received. Re-escalation is at the discretion of the treating physician. In this study, filgrastim or peg-filgrastim may be administered to prevent neutropenia at the discretion of the treating physician.

The use of filgrastim or peg-filgrastim must be documented on the treatment flow sheets. Any toxicities associated with either of these agents must also be documented on the treatment flow sheets.

8.A.3 Impaired Renal Function:

All patients with serum creatinine levels ≤ 1.3 or creatinine clearance (CrCl) > 60 mL/min will receive full doses of all drugs. If the creatinine is 1.4-2.0 or the CrCl is 30-60 mL/min then the doses of cytarabine, etoposide, and cisplatin should all be reduced by 50%. A creatinine clearance of < 30 mL/min will require holding all treatment. Re-escalation to full dose is at the discretion of the treating physician if the serum creatinine level drops to ≤ 1.3 or the CrCl ≥ 50 mL/min.

TABLE 9 Cytarabine, Etoposide & Cisplatin Reductions According to Renal Function

CrCl	Etoposide Dose	Cytarabine Dose	Cisplatin Dose
-------------	-----------------------	-----------------	----------------

> 60 mL/min	100%	100%	100%
30-60 mL/min	50%	50%	50%
10-30 mL/min	0%	0%	0%
< 10 mL/min	0%	0%	0%

8.A.4 Neuropathy:

Patients experiencing Grade 3 cisplatin neuropathy (e.g., loss of motor function) will have the dose reduced by 50% for all further cycles of ESHAP. Patients experiencing Grade 4 neuropathy will have the cisplatin omitted from all further cycles of ESHAP. Patients experiencing Grade 3 cytarabine neuropathy with ESHAP cycle 1 will have the dose reduced by 50% for cycle 2. Patients experiencing Grade 4 or worse cytarabine neuropathy will have the cytarabine omitted from all further cycles.

8.B Rituximab Antibody Toxicities & Dose Modifications

8.B.1 Fevers:

Patients may experience transient fever and rigors with infusion of chimeric anti-CD20 antibody. If Grade 3 fever (or Grade 2 fever with rigors) or Grade 2 rigors are noted, the antibody infusion should be temporarily discontinued, the patient should be observed, and the severity of the side effects should be evaluated. The patient should be treated according to the best available local practices and procedures. Following observation, when fever resolves to Grade 2 or less and rigors to Grade 1 or less, the infusion should be continued, initially, at 1/2 the previous rate. Following the antibody infusion, the IV line should be kept open for medications, as needed.

8.B.2 Hypersensitivity:

Hypotension, bronchospasm or angioedema have occurred as part of an infusion-related symptom complex. If a Grade 3 or greater hypersensitivity/allergic reaction occurs, rituximab infusion should be interrupted and may be resumed at a 50% reduction in rate when symptoms have completely resolved. Treatment with diphenhydramine and acetaminophen is recommended; additional treatment with bronchodilators or IV saline may be used at the physician's discretion. Precautionary hospitalization for patients experiencing severe infusion symptoms which do not resolve after discontinuation of the cycle is recommended.

8.B.3 Observation post Infusion

If there are no complications, the IV line may be discontinued after 1 hour of observation. If complications occur during the rituximab infusion, the patient should be observed for 2 hours after the completion of infusion. If a patient experiences a Grade 3 toxicity that persists until the next scheduled infusion, the patient must discontinue treatment until toxicities have resolved to Grade 2 or less. If treatment is delayed for more than 3 weeks, call the Study Coordinator.

8.B.4 Tumor Lysis Syndrome:

Appropriate medical therapy should be provided for patients who develop tumor lysis syndrome. Following treatment for and resolution of tumor lysis syndrome, subsequent

rituximab therapy may be administered in conjunction with prophylactic therapy for this syndrome. Contact the Study Coordinator prior to resuming treatment in these patients.

TABLE 10
Rituximab Infusion rate Adjustment

Fever	Rigors	Mucosal Congestion/ Edema	% Drop in Systolic BP	Infusion Rate Adjustment
Grade 1	Grade 1-2	Grade 1-2	30 – 49	Decrease By 50%
Grade ≥ 2	Grade ≥ 3	Grade ≥ 3	≥ 50%	Stop infusion*

^{*}Temporarily discontinue infusion until adverse experiences have reversed (generally 15 to 30 minutes) and then resume infusion at 25 - 50% of initial rate.

8.B.5 Hepatitis B Reactivation with Related Fulminant Hepatitis and Other Viral Infections: Carriers of hepatitis B should be closely monitored for clinical and laboratory signs of active HBV infection and for signs of hepatitis throughout their study participation. Patients with any evidence of active hepatic disease or known HBV infection should be managed as clinically appropriate and should only receive rituximab if they have control of the infection and are adequately informed of the risks. Patients who have never received vaccination for HBV, and have not had serologic testing for HBsAg, should be tested for surface antigen positivity.

In patients who develop progressive multifocal leukoencephalopathy (PML), rituximab should be discontinued and reductions or discontinuation of concomitant immunosuppressive therapy and appropriate treatment, including antiviral therapy, should be considered. Physicians should consider PML in any patients presenting with new onset neurologic manifestations, particularly in patients with systemic lupus erythematosis (SLE) or lymphoid malignancies. Consultation with a neurologist, brain MRI, and lumbar puncture should be considered as clinically indicated. There are no known interventions that can reliably prevent PML or adequately treat PML if it occurs.

8.B.6 Severe mucocutaneous reactions:

All patients on or off rituximab therapy should be closely monitored for signs and symptoms suggestive of severe cutaneous and mucocutaneous reactions. Should these symptoms arise, discontinue rituximab therapy (if applicable) and support as clinically indicated.

8.B.7 Cardiovascular events:

Patients with rheumatoid arthritis (RA) are at increased risk for cardiovascular events compared with the general population. Patients with RA should be monitored through the infusion, and rituximab should be discontinued in the event of a serious or life-threatening event.

8.B.8: Arrhythmias:

Patients who develop clinically significant arrhythmias should undergo cardiac monitoring during and after subsequent infusions of rituximab. Patients with pre-existing cardiac conditions including arrhythmias and angina have had recurrences of these events during rituximab therapy and should be monitored throughout the infusion and immediate post-infusion period. Patients

off rituximab therapy should be closely monitored for signs and symptoms suggestive of lifethreatening cardiac events and supported as clinically indicated.

8.B.9 Bowel Obstructions and Perforation:

Complaints of abdominal pain, especially early in the course, should prompt a thorough diagnostic evaluation and appropriate treatment. If the patients experiences a bowel obstruction or perforation, discontinue rituximab therapy. Patients off rituximab therapy should be closely monitored for signs and symptoms suggestive of bowel obstruction and supported as clinically indicated.

8.B.10 Renal:

Discontinuation of rituximab should be considered for those patients with rising serum creatinine or oliguria.

8.C 111In Zevalin & 90Y Zevalin Toxicities & Dose Modifications

The ibritumomab tiuxetan (Zevalin) regimen may cause severe and potentially fatal infusion reactions that usually occur with the first rituximab infusion. Signs and symptoms may include hypotension, angioedema, hypoxia or bronchospasm, and may require interruption of rituximab, ¹¹¹In Zevalin or ⁹⁰Y Zevalin administration. The infusion may be restarted at the physician's discretion.

During the administration of treatment, emergency support for anaphylaxis is to be readily available, including a try for epinephrine, diphenhydramine, hydrocortisone, a laryngoscope, and an endotracheal tube.

8.C.1 Use of Colony Stimulating Factors (CSF) and Platelet and Red Blood Cell Transfusions: Colony Stimulating Factors (CSF) should be administered only in accordance with published ASCO guidelines. Use of CSF under these conditions will be at the discretion of the treating investigator, but must be recorded on the flow sheets.

Platelet transfusions should be administered only in patients with Grade 3 or 4 thrombocytopenia with obvious bleeding. The use of platelet and red cell transfusions under these conditions will be at the discretion of the treating physician, but must be recorded on the flow sheets.

For treatment or dose modification related questions, please contact [name] at [contact].

Unexpected or fatal toxicities (including suspected reactions) must be reported to the Study Coordinator, the ACC DSMB, the IRB, Biogen Idec, and the FDA. The procedure for reporting adverse reactions is outlined in Section 9.

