The administration of rituximab will be accomplished by slow IV infusion. CAUTION: DO NOT ADMINISTER AS AN INTRAVENOUS PUSH OR BOLUS. IV pumps such as the IMED 960 may be used with the rituximab infusion. DO NOT INFUSE CONCOMITANTLY with another IV solution or IV medications. Prime the line with the rituximab solution such that approximately 30 mL are delivered. This will saturate the filter and tubing.

6.C Ibritumomab (IDEC-2B8) Drug Information

6.C.1 Origin of the Ibritumomab (IDEC-2B8) Cell Line

The murine anti-CD20 monoclonal antibody 2B8.H11.G3.G9, ibritumomab (IDEC-2B8), is an IgG₁ kappa antibody. The selection of the monoclonal antibody ibritumomab was based upon observations that: ibritumomab specifically recognized and bound to human B-cell lines and normal human peripheral blood lymphocytes in the same relative proportion as the highly characterized and commercially available anti-CD20 antibodies anti-Leu16 and B1; anti-Leu16 and B1 were effectively inhibited by approximately equal concentrations of ibritumomab; ibritumomab exhibited no cross-reactivity with T-lymphocyte populations.

Ibritumomab was previously expressed by a murine hybridoma cell line and produced in hollow-fiber bioreactors. Currently, ibritumomab is produced in Chinese hamster ovary (CHO) cells in suspension culture. The CHO-expressed ibritumomab antibody differs from the murine hybridoma product in that one amino acid (at position 238 in the heavy chain) has been changed from a lysine to a methionine. The CHO Master Cell Bank has been fully characterized and found to be negative for mycoplasma, infectious virus, and replicating viruses. Types A and C retroviral particles were observed by electron microscopy.

6.C.2 Investigational Drug Nomenclature

• Biogen Idec, Incorporated code designation: Zevalin (Ibritumomab tiuxetan)

• Generic name: Ibritumomab tiuxetan

• IND numbers: BB-IND 4850 - Zevalin

• MF number: BB-MF 7087 - Zevalin

6.C.3 Clinical Formulation

The radiolabeling kit is provided by Biogen Idec and all components are tested to be sterile and pyrogen-free. The kit consists of the following components:

- 3 mL glass vial containing 2 mL (3.2 mg) of Zevalin (ibritumomab tiuxetan) at 1.6 mg/mL in low metal normal saline
- 3 mL glass vial containing 2 mL low-metal 50 mM sodium acetate
- 10 mL glass vial containing 10 mL formulation buffer (PBS containing 7.5% human serum albumin and 1 mM DTPA, pH 7.2)
 - o 10 mL glass vial (empty)

6.C.4 Storage

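### Rituximab stop and restart rules differ between 8.B.1 and Table 10, and 8.A.3 allows full ESHAP dose again inside its own half-dose band

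*Combined protocol and SAP*

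**What the plan says.** **Rituximab.** Section 8.B.1 (Fevers) gives the stop rule: "If Grade 3 fever (or Grade 2 fever with rigors) or Grade 2 rigors are noted, the antibody infusion should be temporarily discontinued". It restarts as follows: "when fever resolves to Grade 2 or less and rigors to Grade 1 or less, the infusion should be continued", and the rate is half of what was running: "the infusion should be continued, initially, at 1/2 the previous rate".

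Table 10, in the same part of section 8, has columns for fever, rigors, mucosal congestion or edema, and fall in systolic pressure. Its first row reads "Grade 1 Grade 1-2 Grade 1-2 30 – 49 Decrease By 50" (per cent). Its second reads "Grade ≥ 2 Grade ≥ 3 Grade ≥ 3 ≥ 50% Stop infusion". A footnote attached only to the second row sets the restart: "Temporarily discontinue infusion until adverse experiences have reversed", and "then resume infusion at 25 - 50% of initial rate".

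On the rate itself, section 6.B.3 says only this: "The administration of rituximab will be accomplished by slow IV infusion". It gives no starting rate and no step-up schedule.

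**ESHAP.** Section 8.A.3 gives full dose at creatinine 1.3 or less or creatinine clearance (CrCl) above 60 mL/min. It gives half dose of cytarabine, etoposide and cisplatin at creatinine 1.4–2.0 or CrCl 30–60. Table 9 repeats the CrCl bands. The same paragraph lets the physician go back to full dose once creatinine is 1.3 or less or CrCl is 50 or more. Section 6.A.1 separately says that a further cisplatin course waits until a raised creatinine is normal again.

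**The concern.** Staff at the bedside have two rules for one event. With Grade 2 rigors and little or no fever, pausing follows 8.B.1 and continuing at half rate follows Table 10, and nothing says which governs. After a stop, a nurse who restarts under 8.B.1 while fever is still Grade 2 is in a state where Table 10 says stop.

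For ESHAP, the threshold for going back to full dose should show that the kidney has recovered. A threshold of 50 lies inside the band that calls for half dose, so it can be met with no recovery. Cisplatin is nephrotoxic by the protocol's own account in 6.A.1.

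At stake are patient safety, uniform delivery of treatment, and the ability to audit compliance, because one action can obey one section and breach another.

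**Working it through.** The plan states no figure on this point, so the check compares the rules and then does simple dose arithmetic.

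**Step 1: stop rules.** I compared 8.B.1 with Table 10 over fever Grade 0–3 by rigors Grade 0–3 (16 combinations), reading the Grade 2 rigors trigger in 8.B.1 as Grade 2 or higher.

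| Fever | Rigors | 8.B.1 | Table 10 |
|---|---|---|---|
| 0 or 1 | 2 | stop | halve rate |
| 2 | 0 | no stop stated | stop |
| 2 | 1 or more | stop | stop |
| 3 | any | stop | stop |
| 0 or 1 | 3 | stop | stop |
| 0 or 1 | 0 or 1 | no stop | halve rate (nothing if both are 0) |

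They differ on stopping in 3 of 16 combinations. Two are Grade 2 rigors with fever Grade 0 or 1. The third, Grade 2 fever alone, is not counted as a conflict because stopping satisfies both texts.

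**Step 2: rate after isolated Grade 2 rigors.** Let the current rate be C. 8.B.1 pauses, then runs at 0.5C. Table 10 goes straight to 0.5C. The end rate is the same; only the pause differs.

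**Step 3: restart rate where both texts stop** (fever Grade 3 or higher, Grade 2 fever with rigors, rigors Grade 3 or higher). Let the initial rate be R and the rate at reaction kR; k is an assumption, as the documents give no schedule.
- 8.B.1: 0.5kR.
- Table 10: 0.25R to 0.5R.
- Ratio: 0.5k/0.5 = k, up to 0.5k/0.25 = 2k.
- k = 1: 8.B.1 equals the top of the Table 10 range, so one rate satisfies both.
- k = 2: 8.B.1 is 2 to 4 times the Table 10 rate, and no rate satisfies both.

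**Step 4: how often the pause question could arise.** Chills serve as a proxy for rigors.
- Table 5: 82 of any grade minus 1 of Grade 3/4 = 81 of Grade 1–2; 81/349 = 23.2%; 0.232 × 52 = about 12 patients.
- Section 6.B.2 (rituximab at other doses): 38%; 0.38 × 52 = 19.8, about 20 patients.

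Both are ceilings. The Grade 2 share is not given, Table 5 counts all events to 30 days after Zevalin, and not all 52 patients need reach Zevalin. The ranges are 0 to about 12, or 0 to about 20. They concern the pause in Step 2 only, not the ratio in Step 3.

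**Step 5: is the CrCl overlap reachable?** The half-dose band is 30–60 and the re-escalation range is 50 or more, so they overlap at 50–60. Section 4.A.13 excludes CrCl below 50, and neither 5.B.1 nor Appendix A schedules laboratory tests at Cycle 1 Day 1. On scheduled tests, then, anyone halved in Cycle 1 on CrCl had a value of 50–60 and already met the re-escalation threshold.

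**Step 6: dose at stake.** Doses are from Table 7, in mg/m².

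| | Cisplatin | Cytarabine | Etoposide |
|---|---|---|---|
| Full cycle | 25 × 4 = 100 | 2000 | 40 × 4 = 160 |
| Half cycle | 50 | 1000 | 80 |
| Planned, two cycles | 200 | 4000 | 320 |
| Half + half (50% of plan) | 100 | 2000 | 160 |
| Half + full (75% of plan) | 150 | 3000 | 240 |

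**Step 7: statistical design.** Sections 4.C and 12.B analyse every patient with at least one dose of chemotherapy. The sample size rests on 50% versus 67.3% at one-sided 0.10 and 90% power. No dosing or infusion rule enters it.

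**The case against.** Much of the opposing case stands.

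- **Isolated Grade 2 rigors.** Both texts end at half the current rate, so the disagreement is a short pause. A reader might infer that these patients face restart rates several times apart. The documents do not support that: the 25–50% footnote belongs to the stop row only, Grade 2 rigors sit in the other row, and any k above 1 is assumed.
- **Restart condition.** Waiting for full reversal satisfies both texts, so a compliant course exists. What remains is that 8.B.1 directs a restart at a fever grade where Table 10 directs a stop.
- **Physician discretion.** Section 8.C leaves restart of the infusion to the physician. It gives no grade or rate and does not rank 8.B.1 against Table 10.
- **Differences between sites.** A reader might infer that two sites would treat the same reaction differently. Section 12.A still describes two institutions, but 13.A.1 names one IRB of record, so this is not established. Staff at one site can differ just as well.
- **ESHAP.** A reader might infer that full-dose cisplatin will be given to patients with impaired kidneys. That is too strong. Re-escalation is discretionary, and only BUN and creatinine are the scheduled renal tests before Cycle 2 (5.B.2). If creatinine is 1.4–2.0 and counts as elevated (6.A.1 does not define normal), 6.A.1 holds the course. If it is 1.3 or less, the first sentence of 8.A.3 already gives full dose while the CrCl band gives half. The gap is therefore mainly for patients with normal creatinine and CrCl 50–60. It survives there, because the 6.A.1 hold depends on creatinine and not on CrCl.

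**Conclusion.** The inconsistencies are real in the current text, and no other section settles them. They warrant a minor safety wording correction.

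For rituximab, the size is a pause or no pause for isolated Grade 2 rigors. For reactions where both texts stop, there is also a different restart condition, and a different restart rate if the rate had been raised. For ESHAP, it is 75% rather than 50% of the planned two-cycle dose for a patient halved in Cycle 1 at CrCl 50–60, where the 6.A.1 hold does not apply.

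The number of patients affected is not given and may be small, possibly none. The conclusion rests on reading 8.B.1 and Table 10 as both in force and on scheduled tests only at Cycle 1. A reader might infer damage to the trial's statistical design; the documents do not support that, since sample size, alpha and power are unchanged.

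**What to change.** **8.B.1 and Table 10.** Use one rule in both: stop for rigors Grade 2 or higher or fever Grade 2 or higher; restart only when both are Grade 1 or less, at 25–50% of the initial rate. Move Grade 2 rigors to the stop row of Table 10 and reword its footnote to match.

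**8.A.3.** Change the CrCl threshold for re-escalation from 50 or more to above 60 mL/min. Add that the lower dose applies if creatinine and CrCl point to different doses.

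**6.A.1 and 8.A.3.** State whether the creatinine hold or the half dose governs Cycle 2 at creatinine 1.4–2.0. At present one text withholds the course and the other gives half of it.

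The clinical team should confirm every threshold. The restart condition of Grade 1 or less needs particular attention, because it lies between the two existing conditions.

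The cost is a wording amendment with no added visits or tests. The downside is slightly more infusion pauses and fewer full-dose second cycles. If treatment has ended, the useful step is to record which rules were applied.
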